7.2 Response Criteria for Patients with Chronic Lymphocytic Leukemia

Criteria for response will utilize the IWCLL Guidelines for response, which includes clinical, hematological, and bone marrow features as outlined below (Hallek et al., 2008).

Minimal Residual Disease negative: less than 0.01% CLL cell involvement by 4-color flow cytometry of bone marrow aspirate (less than 1 in 10,000 events) and meeting all other criteria for complete response.

Complete response: Requires all of the following for a period of at least two months from completion of therapy:

- Absence of significant lymphadenopathy (e.g. >1.5cm in diameter) on physical exam;
- No hepatomegaly or splenomegaly on physical exam;
- Absence of constitutional symptoms;
- Blood counts corresponding to the following values: Lymphocytes < 4,000/uL, polymorphonuclear leukocytes >1500/μL, platelets >100,000/μL, hemoglobin >11.0 g/dL (untransfused)
- Bone marrow aspirate and biopsy must be normocellular for age with <30% of nucleated cells being lymphocytes. Lymphoid nodules must be absent. If the marrow is hypocellular, a repeat determination should be performed in one month.
- The marrow should be analyzed by flow cytometry and/or immunohistochemistry to demonstrate that the marrow is free of clonal B- CLL cells.
- A CT scan or MRI documenting absence of significant lymphadenopathy should be performed if previously abnormal.
- Patients who fulfill the criteria for CR with the exception of a persistent cytopenia
 that is believed to be treatment related will be considered CR with incomplete bone
 marrow recovery (CRi). Additionally, patients who fulfill the criteria of CR with
 exception of having bone marrow lymphoid nodules will be considered a nodular
 PR.

Partial response: Requires at least 2 of the following criteria from group A, and at least one of the criteria from group B, and for a period of at least 2 months: Group A:

- ≥50% decrease in peripheral absolute lymphocyte count from pretreatment value, or less than 4,000/uL.
- ≥50% reduction in lymphadenopathy by examination or scan, or less than 1.5cm in size.
- ≥50% reduction in splenomegaly (cm below costal margin) by examination or scan
- ≥50% reduction hepatomegaly (total liver span) by examination or scan
- ≥50% reduction in marrow infiltrate or B-lymphoid nodules

Group B:

- Polymorphonuclear leukocytes ≥1,500/µL or 50% improvement from pre-treatment value;
- Platelets >100,000/µL or 50% improvement from pre-treatment value;
- Hemoglobin >11.0 g/dl (un-transfused) or 50% improvement from pre-treatment value.

Progressive Disease: Characterized by any one of the following events:

- ≥50% increase in the products of at least two lymph nodes on two consecutive determinations two weeks apart (at least one lymph node must be ≥2 cm); appearance of new palpable lymph nodes.
- ≥50% increase in the size of the liver and/or spleen as determined by measurement below the respective costal margin; appearance of palpable hepatomegaly or splenomegaly, which was not previously present.
- An increase in the number of blood lymphocytes by 50% or more with at least 5000 B lymphocytes per microliter.
- Transformation to a more aggressive histology (i.e., Richter's syndrome or prolymphocytic leukemia with ≥56% prolymphocytes).
- During therapy, patients not fulfilling the above criteria for progressive disease but demonstrating a decrease in hemoglobin >2 gm/dL, decrease >50% in platelet or granulocyte count will not be rated as progressive disease because these may occur as both a consequence of therapy. A bone marrow biopsy in such settings is strongly encouraged. Furthermore, during therapy, patients with progressive lymphocytosis but not any other findings of hemoglobin, platelet count, lymph node size, or spleen size meeting criteria for progressive disease will not be rated as progressive disease as agents that target the akt pathway have been demonstrated to induce a redistributive lymphocytosis as part of the mechanism of action (Byrd et al., 2013).
- After treatment, The progression of any cytopenia (unrelated to autoimmune cytopenia), as documented by a decrease of Hgb levels by more than 20 g/L (2 g/dL) or to less than 100 g/L (10 g/dL), or by a decrease of platelet counts by more than 50% or to less than 100 × 10⁹/L (100 000/µL), which occurs at least 3 months after treatment, defines disease progression, if the marrow biopsy demonstrates an infiltrate of clonal CLL cells.

Stable Disease: Patients who do not fulfill the criteria for complete or partial response as defined above but do not exhibit progressive disease will be considered as having stable disease.

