1.4 Rationale for Dose Selection

Each extension course consists of 8 infusions. A patient may repeat the course, and therefore receive a total of 16 infusions on the extension study. Each individual patient will receive the same

dosage of UC-961 for each of the 8 infusions of each course. The dosage of UC-961 may be increased for the 2nd set of 8 infusions (if a higher dose has been shown to be safe on the phase 1 trial AND there is Progressive Disease or Stable Disease after the first course of extension.

The dose administered on this extension study will be the highest safe dose, or once established, the biologically active dose or the recommended phase 2 dose from the phase 1 trial. To date, the 8 mg/kg dose level has been completed and determined to be safe. Therefore, patients on this extension study will begin at the 8 mg/kg dose level. Should subsequent dose levels be determined to be safe in the Phase 1 trial, the dose utilized in this trial may increase for subsequent patients.

Planned dose levels (starting dose is the highest safe dose administered to a patient in the phase 1 trial):

Potential	Dose		
Dose Level			
-1	4 mg/kg		
1 (start)	8 mg/kg		
2	16 mg/kg (or max 2000 mg dose)		
3	20 mg/kg (or max 2000 mg dose)		

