6.0 Schedule of Events

Treatment Cycle	Screening	Extension Course 1	Response Assessment 1	Extension Course 2	Response Assessment 2	Long-Term Follow-up
Visit Day		1, 15, 29, 43, 57, 85, 113, 141	169 ⁶	197, 211, 225, 239, 253, 281, 309, 337 ⁷	365 ⁶	Q28d x8, then q56d
Visit window	≤ 30 days prior to visit 2	±3d	±7d	±3d	±7d	±7d
Informed Consent	X					
Eligibility Checklist	Х					
History and Symptoms	Х	Х	Х	Х	X	Х
VS/Ht and Wt	Х	Х	Х	Х	X	Х
Comprehensive PE	Х	Х	X	Х	X	Х
ECOG Performance Status	X	Х	Х	Х	Х	Х
CBC and differential	×	X	X	X	X	X
Blood chemistry panel ¹	Х	Х	Х	Х	Х	Х
ECG	Х					
Adverse Events Screen		Х	Х	Х	Х	Х
Concomitant Medication		Х	X	Х	X	Х
UC-961 Administration		Х		X		
CT scan Chest/ Abdomen/ Pelvis ²	within 60 days of C1D1		Х		Х	
Bone marrow aspirate and biopsy ³	within 90 days of C1D1		Х		Х	
Cytogenetics/FISH from bone marrow or peripheral blood ⁴	X		×		Х	
Serum hCG for female	within 14 days of C1D1					
of child bearing potential Quantitative T-cell subsets	X		Х		Х	

Treatment Cycle	Screening	Extension Course 1	Response Assessment 1	Extension Course 2	Response Assessment 2	Long-Term Follow-up
Visit Day		1, 15, 29, 43, 57, 85, 113, 141	169 ⁶	197, 211, 225, 239, 253, 281, 309, 337 ⁷	365 ⁶	Q28d x8, then q56d
Visit window	≤ 30 days prior to visit 2	±3d	±7d	±3d	±7d	±7d
PT/aPTT	X					
Collection of Pharmacokinetic and Pharmacodynamic Samples ⁵	Х	Х	PD only	Х	PD only	PD only

- 1. Chemistry panel to include: comprehensive metabolic panel (Na+, Cl-, K+, CO2, BUN, Creatinine, Glucose, Ca2+, total protein, albumin, total bilirubin, SGPT, SGOT, alkaline phosphatase), phosphorous, magnesium, uric acid, LDH, amylase, and lipase. NOTE: amylase and lipase are not measured in long-term follow-up unless clinically indicated.
- 2. Or MRI or PET scan.
- 3. In the case of a CR, an additional bone marrow will be taken two months after patient first achieves CR
- 4. Chromosome analysis and FISH Panel to include 11q, 12p, 13q, 17p analysis.
- 5. Blood samples are collected for PK and/or PD analysis (refer to section 5.8 and 5.9)
- 6. May be done earlier if progressive disease is suspected.
- 7. Or 28 days after Response Assessment 1.

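### CR, CRi, MRD-negative and nodular PR as defined in Section 7.2 cannot be satisfied by Day 169 in a patient dosed on schedule, and the plan does not say whether the visit call is provisional

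*Combined protocol and SAP*

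**What the plan says.** **CR and the categories built on it (Section 7.2).** The CR list opens with "Requires all of the following for a period of at least two months from completion of therapy". MRD-negative status needs all other CR criteria. CRi is CR apart from a persistent cytopenia "that is believed to be treatment related will be considered CR with incomplete bone" marrow recovery. A patient who meets CR with the "exception of having bone marrow lymphoid nodules will be considered a nodular" PR. None of the three waives the timing condition.

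**PR and stable disease (Section 7.2).** PR needs two group A criteria "and at least one of the criteria from group B, and for a period of at least 2 months", with no link to the end of therapy. Stable disease is the default: "Patients who do not fulfill the criteria for complete or partial response as defined above but do not exhibit progressive disease".

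**Schedule (Sections 4.5, 5.2 to 5.4, 6.0).** Course 1 ends with the Day 141 dose (±3 days) and response is assessed on Day 169 (±7). Course 2 runs from Day 197 to Day 337 (±3 in Section 6.0, ±7 in Section 5.4), with the second assessment on Day 365 (±7). Footnote 7 gives another Course 2 start: "Or 28 days after Response Assessment 1". Footnote 6 lets an assessment come earlier if progression is suspected. Course 2 is optional (Section 1.4): "A patient may repeat the course, and therefore receive a total of 16 infusions on the extension study".

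**Later data.** Footnote 3 of Section 6.0 reads: "In the case of a CR, an additional bone marrow will be taken two months after patient first achieves CR". Follow-up (Section 5.5) has examinations and blood counts every 28 days for 8 visits, but no scheduled imaging.

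**Use of the response status.** Section 4.1 and the synopsis use CR/PR versus stable or progressive disease after Course 1 to branch Course 2. Sections 2.5 and 10.0 list ORR after 6 months of dosing as a secondary endpoint.

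**The concern.** The definition and the visit calendar do not fit together. Section 7.2 starts a two-month clock at completion of therapy, while the assessment comes four weeks after the last dose of the course. Yet Section 4.1, the synopsis and footnote 3 all take it that a CR can be called at or around that assessment.

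Two analysts could therefore produce different tables from the same data. One applies Section 7.2 as written and, at Day 169, records no CR, CRi, MRD-negative or nodular PR among patients dosed on schedule, with late partial responders placed in stable disease. The other records whatever criteria are met on the day. A reader of the reported rates could not tell which was done. The same status also feeds the Course 2 branch, so the ambiguity reaches beyond reporting.

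**Working it through.** **Reproducing the calendar.** Each of the first four doses is followed by 14 days and the later ones by 28.
- Course 1: 1 + 4×14 + 3×28 = Day 141; 141 + 28 = Day 169.
- Course 2: 197 + 4×14 + 3×28 = Day 337; 337 + 28 = Day 365.

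Both match Section 6.0.

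**Yardstick.** The documents do not give two months in days. I use 56 days (8 weeks, the most lenient reading) and 61 days (a calendar average; the range is 59 to 62).

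**Last dose to assessment**

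| Interval | Nominal | Range with windows | Shortfall at the longest gap, against 56 / 61 days |
|---|---|---|---|
| Course 1 to Day 169 | 169 − 141 = 28 | 162 − 144 = 18 to 176 − 138 = 38 | 18 / 23 |
| Course 2 to Day 365, ±3 doses, footnote 7 | 365 − 337 = 28 | 358 − 347 = 11 to 372 − 327 = 45 | 11 / 16 |
| Course 2 to Day 365, ±7 doses, footnote 7 | 28 | 358 − 351 = 7 to 372 − 323 = 49 | 7 / 12 |

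For the footnote 7 rows, Assessment 1 on Day 162 to 176 puts the Course 2 start on Day 190 to 204 and its last dose 140 days later, on Day 330 to 344, before the dose window is applied.

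**Exception at Day 365.** Suppose footnote 6 brings Assessment 1 forward to, say, Day 148. Course 2 then starts on Day 148 + 28 = 176 and ends on Day 176 + 140 = 316. If Assessment 2 stays at Day 365, the gap is 49 days, and at the window extremes 372 − 313 = 59 (±3) or 372 − 309 = 63 (±7). This narrow case can pass 56 days.

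**If therapy is complete after Course 1.** Day 365 is 365 − 141 = 224 days after the last dose (358 − 144 = 214 to 372 − 138 = 234), so the condition can be met if that visit takes place.

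**PR: time from first documentation to Day 169**

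| First seen | Nominal | Range | 2 months by Day 169? |
|---|---|---|---|
| Day 85 | 84 | 74–94 | yes |
| Day 113 | 56 | 46–66 | borderline |
| Day 141 | 28 | 18–38 | no |
| Day 169 scan or marrow | 0 | – | cannot be shown |

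No scan or marrow is scheduled between screening and Day 169, so a PR that needs one has no earlier documentation.

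**Where the footnote 3 marrow falls**
- After Day 169: 169 + 56 to 169 + 61 = Day 225 to 230. This is during Course 2 if it is given, or 84 to 89 days after Day 141 if it is not.
- After Day 365: Day 421 to 426, which is 84 to 89 days after Day 337 and consistent with Section 7.2.
- The footnote applies only to CR, so a marrow-dependent PR or a nodular PR has no scheduled repeat.

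**Weight of one patient in the ORR.** 1/33 = 3.0 points; 1/75 = 1.3 points.

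**The case against.** The strongest reply is that the plan intends a call at the visit with confirmation afterwards. Sections 2.5 and 10.0 do not say that the category must be final on Day 169, and a duration condition can be met by later data. Footnote 3 speaks of the first achievement of CR and then repeats the marrow. Section 4.1 has a CR branch after Course 1 that would otherwise be empty for patients dosed on schedule. On this view one sentence is missing, and no category is unattainable.

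Much of this stands. A reader might infer that the reported CR and MRD-negative rates must be zero. The documents support that only for a Day 169 snapshot read literally, and they never name that snapshot as the endpoint. A reader might also infer that ORR is forced to zero; it is not, because a PR on examination and blood counts seen by Day 85 qualifies at Day 169. Nor is it right that no permitted timing reaches two months at Day 365, given the early-assessment case. A scan-dependent PR may in fact have lasted two months; the accurate statement is that this cannot be shown. Section 7.2 also accepts node, spleen and liver reduction by examination, so many PRs need no repeat scan.

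The reply does not supply the missing rule. Nothing calls the Day 169 or Day 365 status provisional, fixes a confirmation date, or says when a confirmed response enters the ORR.

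**Conclusion.** The point holds in this form. For a patient dosed on schedule, CR, CRi, MRD-negative status and nodular PR cannot be satisfied by Day 169: the gap is 28 days, at most 38, against 56 to 61. The same applies at Day 365 if both courses are given, completion of therapy means the last Course 2 dose, and Assessment 1 was within its window (at most 45 or 49 days). A PR first seen after about Day 113, or dependent on the Day 169 scan or marrow, cannot be shown to have lasted 2 months by Day 169.

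Read literally, a patient in these groups who has no PR already held for 2 months, and no progression, is stable disease. That conflicts with the status that Section 4.1, the synopsis and footnote 3 assume.

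The size of the affected group cannot be derived from the documents. The endpoints are secondary and descriptive in a safety study, so this should be fixed but does not undermine the primary aim.

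Three nearby conflicts are separate and are not needed for this conclusion: the marrow is conditional in Section 5.3.7 but marked at both assessments in Section 6.0; the dose increase is stated as what happens in Section 4.1 but as eligibility in the synopsis; and the Course 2 window is ±7 days in Section 5.4 but ±3 in Section 6.0. Each needs reconciling.

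**What to change.** For the secondary descriptive endpoints:

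1. In Section 7.2, define completion of therapy for patients who receive one course and for those who receive two, and state two months in days (56 or 61).
2. In Section 10.0, report two results side by side in all treated patients: (a) criteria met at the Day 169 and Day 365 visits, and (b) response that meets the Section 7.2 duration. Use the examinations, blood counts and footnote 3 marrow already scheduled. Flag confirmations obtained during Course 2 as on-treatment, because they do not run from the end of therapy if Course 2 counts as therapy. List scan- or marrow-dependent responses with no repeat as unconfirmed, with their number.
3. Reconcile Section 7.2, footnote 3 of Section 6.0, Section 4.1 and the synopsis on which response status is meant. Which status governs Course 2 is for the investigators to decide.

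The cost is wording and a second tabulation, with no added visits, scans or marrows. The downside is that some visit responses will stay unconfirmed, particularly those that depend on a scan, since none is scheduled in follow-up.

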3.0 PATIENT ELIGIBILITY

3.1 Inclusion Criteria

Subjects must meet all of the inclusion criteria to participate in this study.

- **1.** Ability to understand and the willingness to sign a written informed consent.
- 2. Clinical and phenotypic verification of B cell CLL and measurable disease. Immunophenotyping of the leukemic cells (blood or marrow) must demonstrate a monoclonal (or light chain positive) B cell population with immunophenotype consistent with CLL (e.g., co-expressing CD19 and CD5).
- **3.** Recovered from toxic effects attributed to UC-961 to grade 1 levels, or baseline.
- **4.** Must have measurable disease, including one of the following: absolute lymphocyte count greater than 5000/uL, lymphadenopathy greater than 1.5cm in longest dimension, splenomegaly (palpable at least 1 cm below the costal margin or radiographically enlarged), bone marrow biopsy with residual CLL cells, or resultant bone marrow dysfunction (platelet count < 100k /uL, hemoglobin < 10 g/dL).
- **5.** Women of childbearing potential (not postmenopausal for at least one year or not surgically incapable of bearing children) must agree not to become pregnant for the duration of the study. Both men and women must agree to use a barrier method of contraception for the duration of the study and until 10 weeks after the final dose of UC-961 (expected to be greater than 5 half-lives from pre-clinical data).
- **6.** Subjects must have an ECOG performance status of 0-2.
- **7.** Adequate hematologic function:
 - Platelet count ≥ 50,000/µL unless due to heavily infiltrated bone marrow (> 80% CLL cell infiltrate); AND
 - Hemoglobin ≥ 8.0 g/dL (may be supported by erythropoietin); AND
 - Absolute neutrophil count > 1000 /uL unless due to heavily infiltrated bone marrow (> 80% CLL cell infiltrate).
- 8. Adequate renal function:
 - Serum creatinine <1.5 times upper limit of normal; OR
 - Calculated Creatinine clearance (CrCl) ≥ 40 mL/min (based upon the Cockcroft-Gault Equation [CrCl = (140-age) * actual wt (in kg) * (0.85 if female) / (72 * Cr)].
- **9.** Adequate hepatic function:
 - Total bilirubin ≤ 2.5 times upper limit of normal; AND
 - ALT ≤ 2.5 times upper limit of normal.
- **10.** Adequate coagulation tests:
 - Prothrombin time international normalized ratio (INR) ≤ 2; AND
 - Partial thromboplastin time ≤ 1.66 times upper limit of normal.

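### Section 7.2 scores any newly palpable lymph node as progressive disease with no size floor, so a node the protocol elsewhere treats as not significant can become a PFS event

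*Combined protocol and SAP*

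**What the plan says.** Section 7.2 opens its list with "Progressive Disease: Characterized by any one of the following events", so one item is enough. The nodal bullet has two limbs. The growth limb is "≥50% increase in the products of at least two lymph nodes on two consecutive determinations two weeks apart", with one node of at least 2 cm. The second limb follows a semicolon: "at least one lymph node must be ≥2 cm); appearance of new palpable lymph nodes". It has no size and no repeat determination.

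Three other places set a nodal size:

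- CR in 7.2: "Absence of significant lymphadenopathy (e.g. >1.5cm in diameter) on physical exam".
- PR Group A in 7.2: lymphadenopathy reduced to under 1.5 cm satisfies the nodal item.
- Inclusion criterion 4 in 3.1: measurable disease includes "lymphadenopathy greater than 1.5cm in longest dimension, splenomegaly (palpable at least 1 cm below the costal margin or radiographically enlarged").

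Section 7.2.1 makes objective tumor progression or death the PFS event and does not say what makes a progression objective. Section 10.0 reports PFS and the response categories descriptively, with 95% confidence intervals and no hypothesis tests.

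**The concern.** Within one bullet, growth of known disease is protected by a size floor and a second determination, while the new-node limb has neither. The missing floor conflicts with the nodal size used for response and for eligibility. Small palpable nodes can have causes other than CLL, and nodes are examined at every visit, so there are many chances to record one.

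PD ends PFS and excludes a patient from SD by definition. Section 7.2 does not say whether PD overrides a concurrent PR. If it does, the PR rate falls too. With about 33 patients anticipated, a few such events would visibly move a Kaplan-Meier curve. PD also enters treatment decisions in 4.1 (dose for course 2) and 4.9 (end of treatment), so the definition has effects beyond the analysis.

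**Working it through.** The plan gives no PFS event count, precision target or misclassification rate, so there is no figure to reproduce. The check compares the criteria and then illustrates the size.

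**1. One case under each rule.** Take a patient with no other enlarged nodes and one new palpable node of 1.4 cm.

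| Rule | Size condition | Result |
|---|---|---|
| CR, nodal condition (7.2) | only nodes above 1.5 cm are significant | condition met |
| PR Group A, nodal item (7.2) | under 1.5 cm suffices | a residual node of this size counts toward response |
| Inclusion 4 (3.1) | above 1.5 cm | not measurable by nodes |
| PD, growth of known nodes (7.2) | one node at least 2 cm, two determinations | not met |
| PD, new node (7.2) | none | PD on one examination |

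The nodal condition for CR and the definition of PD are both met at the same visit.

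**2. Does anything downstream correct this?** Section 7.2.1 adds no confirmation, imaging or review. Footnote 6 in Section 6.0 lets the response assessment be brought forward when progression is suspected, but does not require it. CT is scheduled at screening, Day 169 and Day 365. Long-term follow-up (5.5) has examinations and no scheduled imaging.

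**3. Direction.** Every finding that is PD with a size floor is also PD without one. For a given series of examinations, the PD date under the present wording is therefore the same or earlier, never later.

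**4. Number of examinations (5.2 to 5.4 and 6.0).** After Day 1: 7 infusion visits (Days 15, 29, 43, 57, 85, 113, 141) + Day 169 = 8. Adding 8 course 2 infusion visits and Day 365 gives 8 + 8 + 1 = 17.

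**5. Illustration.** Let f be the chance, per examination, of recording a new node of 1.5 cm or less in a patient without true progression. The documents do not give f; the range below is assumed. With independent examinations, the chance of at least one such finding in k examinations is 1 − (1 − f)^k.

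| f (assumed) | k = 8, Day 169 | k = 17, Day 365 | Expected among 33 by Day 365 |
|---|---|---|---|
| 0.5% | 1 − 0.995^8 = 3.9% | 1 − 0.995^17 = 8.2% | 33 × 0.0817 = 2.7 |
| 1% | 1 − 0.99^8 = 7.7% | 1 − 0.99^17 = 15.7% | 33 × 0.1571 = 5.2 |
| 2% | 1 − 0.98^8 = 14.9% | 1 − 0.98^17 = 29.1% | 33 × 0.2907 = 9.6 |

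These are upper-end figures. They keep every patient under examination throughout, although course 2 is optional and patients leave earlier for progression, toxicity or new therapy.

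**The case against.** The strongest reply is that 1.5 cm is not a PD threshold. CR uses it, with an e.g., for residual nodes, and inclusion 4 uses it for entry. Neither says that a small new node in a CLL patient is harmless. CR also requires all its conditions for two months, so nobody is finally classed as both CR and PD. This stands as far as it goes: the overlap is in the nodal condition at one visit, not in a final category. It does not explain why new disease needs no size when growth of known disease needs 2 cm.

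Section 7.2 also says it follows the cited iwCLL guideline. Whether the new-node wording matches that source cannot be checked from these documents. The inconsistency is within the protocol either way.

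PFS is secondary and descriptive. That is correct, and it limits the consequence to the estimates; no error rate or power is affected.

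A reader might infer more than the text supports:

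- *That a spleen going from 1.0 to 1.5 cm is PD below the protocol's own threshold.* The change is 1.5/1.0 − 1 = 50%, so it meets "≥50% increase in the size of the liver and/or spleen as determined by measurement below the respective costal margin". But the only spleen size in the documents is the 1 cm in inclusion 4, which both values meet. The PD criteria set no spleen floor to fall below.
- *That a spleen enlarged only on imaging at entry becomes PD once it is felt.* The limb reads "appearance of palpable hepatomegaly or splenomegaly, which was not previously present". Inclusion 4 counts radiographic enlargement as splenomegaly, so it may already have been present. The text can be read either way.
- *That every palpation finding should need confirmation at the next visit.* That is a trade-off, not a correction. It needs a rule for patients who are not re-examined, it leaves a persistent 1.5 cm spleen as PD, and it would delay a call on which treatment decisions depend.
- *That false PFS events are shown to occur.* They are a risk created by the wording; no error rate is documented.

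**Conclusion.** The point holds for new lymph nodes. As written, one examination finding a new palpable node of any size is PD and hence a PFS event, although the protocol elsewhere treats nodes of 1.5 cm or less as neither significant nor measurable. Compared with a definition that has a floor, the present one can only bring PD forward. How far this biases PFS and the SD and PR rates depends on how often small new nodes are felt and how many are not CLL, which the documents do not say. The 8% to 29% by Day 365 is an illustration resting on an assumed 0.5% to 2% per visit, independence between visits and full attendance at 17 visits. The effect is confined to secondary, descriptive endpoints; the primary safety assessment is untouched.

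**What to change.** In 7.2, state that for scoring PD in the response and PFS analyses a new lymph node counts only when it exceeds 1.5 cm in longest dimension, the figure already used in inclusion 4. State also that a smaller new node is recorded and counts from the first examination at which it exceeds that size.

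The change takes one or two sentences and needs no extra visits or tests, since organ and node measurements are already part of each examination. The downside is that a true progression first appearing as a small node is dated slightly later.

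Sections 4.1 and 4.9 use PD for treatment decisions, so the sponsor should reconcile them with the revised scoring definition and say whether one definition serves both purposes. If they differ, a patient who starts new therapy after a small-node finding leaves follow-up under 4.10 without a scored PFS event, and the analysis should say how that patient is handled. No clinical rule is proposed here.
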